3. STUDY DESIGN

3.1.OVERALL STUDY DESIGN

This is a multicenter, prospective phase Ib trial based on a dose escalation study design assessing four dose levels of Olaparib given with concomitant radiotherapy, followed by an expansion cohort once the recommended phase II dose (RP2D) has been established.

3.2.RATIONALE FOR STUDY DESIGN AND DOSES

Few clinical data about combination of Olaparib and radiotherapy are available and more or less about Olaparib and STS radiotherapy. Therefore, a phase 1 dose escalation trial has been designed in order to determine the MTD and the safety of the combination. An expansion cohort should allow to appreciate anti-tumor activity of the combination.

Study population was defined as patients with locally advanced/unresectable STS (with or without metastases) because their outcome with radiotherapy alone is very poor.

The choice of olaparib doses was based on preclinical data showing that low doses are sufficient with radiotherapy.

3.3.DEFINITIONS

Dose-limiting toxicity (DLT)

A DLT is defined as an adverse event (AE) or laboratory abnormality that fulfills all the criteria below:

- Occurs during the period of observation of DLTs defined as the period between the first day of treatment administration and up to 6 weeks after the end of radiotherapy.
- Is considered to be at least possibly related to the treatment strategy (radiotherapy or Olaparib).
- Is unrelated to disease, disease progression, inter-current illness, or concomitant medications.
- Meets one of the criteria below, graded as outlined or according to NCI CTCAEv4.0:
 - Any grade ≥ 3 musculoskeletal or cutaneous toxicity within the field of radiation:
 - Occurring at a radiotherapy dose $< 30\text{Gy}$
 - Occuring at a radiotherapy dose $\geq 30\text{Gy}$ and without regress to a grade ≤ 2 in a time limit of 4 weeks
 - Any non-hematological toxicity \geq grade 3 (except for nausea, vomiting, fatigue, alopecia and fever)
 - Laboratory abnormality \geq grade 3 lasting > 5 days (except for lymphopenia, hyperglycaemia and changes in serum electrolytes/enzymes without clinical impact)

- Febrile neutropenia (absolute neutrophil count [ANC] < 1.0 x10⁹/L and fever ≥ 38.5°C) and/or documented infection with ANC < 1.0 x 10⁹/L
- Grade 4 neutropenia (absolute neutrophil count < 500) lasting ≥ 7 days
- Grade 4 thrombocytopenia or bleeding requiring a platelet transfusion
- Any other toxicity grade ≥ 4

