- Any other study drug related toxicity considered significant enough to be qualified as DLT in the opinion of the investigators after discussion with the sponsor.

In addition, the following events, in case they are related to the toxicity of the treatments, will also be considered as DLT:

- Interruption of radiotherapy for seven consecutive days or longer,
- Interruption of Olaparib for 14 days or longer, whether this interruption happens on consecutive days or not.

A **DLT validation committee** will be consulted before the first escalation to a new dose level (see section 12.1.2).

Maximum tolerated dose (MTD)

The MTD for Olaparib is defined as the dose at which an unacceptable frequency of DLT is observed (33%). Conclusions of the steering committee for the definition of the MTD will be submitted to an independent committee (IDMC) before opening the expansion cohort.

Recommended phase II dose (RP2D)

The RP2D dose corresponds to the dose level to be recommended for further investigations in phase II trials. The RP2D dose for Olaparib will be identified by the steering committee based on the MTD for Olaparib as defined following the dose escalation trial, as well as additional safety data, including acute and late toxicities, PK and PD data. Data from all patients (dose escalation trial and expansion cohort) will be used to define the RP2D.

3.4.DOSE ESCALATION PART

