9. AEs	As per NCI-CTCAE, version 4.	Throughout the treatment period

*For all laboratory tests a window of 72 hours will be allowed.

ALT, alanine aminotransferase; ANC, absolute neutrophil count; AP, alkaline phosphatase; aPTT, activated partial thromboplastin time;

	ASSESSMENT	TIME
AST, aspartate aminotransferase; ECG, electrocardiogram; ECOG PS, Eastern Cooperative Oncology Group Performance Status; INR, International Normalized Ratio; LDH, lactate dehydrogenase; MCH, mean cell haemoglobin; MCHC, mean cell haemoglobin concentration; MCV, mean cell volume; MRI, magnetic resonance imaging; RBC, red blood cell; RECIST v1.1, Response Evaluation Criteria In Solid Tumors; TP, prothrombin Rate; WBC, white blood cells.		

5.6.EVALUATION AT END OF TREATMENT

The end-of-treatment visit will be scheduled:

- 30 days (4 weeks) after the last Olaparib administration (a window of ± 1 week is allowed) and/or
- 6 weeks after the last dose of radiotherapy.

Regardless of the reason for discontinuation, the complete workup has to be done at the end-of-treatment visit. This will include the following assessments:

- Assessment of signs and symptoms.
- Complete physical examination.
- ECOG performance status.
- Vital signs [heart rate, blood pressure, and temperature].
- Hematology.
- Biochemistry.
- Calculated CrCl.
- Electrocardiogram (QTc measurement: twelve-lead ECGs will be obtained after the patient has been rested in a supine position for at least 5 minutes. ECGs will be recorded at 25 mm/sec.)
- Clinical and radiological tumor assessment (MRI and CT Scan if metastatic disease at inclusion) (except for patients with confirmed PD at discontinuation or who had started a new treatment).
- Intercurrent events and concomitant disease and treatments.
- Safety assessment (AEs).

Adverse events must be reported for 30 days after the last dose of Olaparib and/or 6 weeks after the last dose of radiotherapy administration or until the start of a new antitumor therapy, whichever occurs first. All SAEs occurring within 30 days after the last dose of Olaparib and/or 6 weeks after the last dose of radiotherapy or until the start of a new antitumor therapy, whichever occurs first, will be reported. Beyond this period of time, only those SAEs suspected to be treatment-related (Olaparib/radiotherapy) or research-related (diagnostic procedures, examinations carried out during the research...) will be reported (see Section 11).

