11.2.2. Serious adverse event

A serious adverse event is an AE occurring during any study phase (i.e., screening, run-in, treatment, wash-out, follow-up), at any dose of the study drugs that fulfils one or more of the following criteria:

- Results in death
- Is immediately life-threatening
- Requires in-patient hospitalization or prolongation of existing hospitalization
- Results in persistent or significant disability or incapacity
- Is a congenital abnormality or birth defect
- Is an important medical event that may jeopardize the patient or may require medical intervention to prevent one of the outcomes listed above.

The causality of SAEs (their relationship to all study treatment/procedures) will be assessed by the investigator(s) and communicated to Sponsor.

Any suspected transmission via a medicinal product of an infectious agent, pathogenic or non-pathogenic, is assessed as a serious adverse event with the seriousness criterion important medical event. The event may be suspected from clinical symptoms or laboratory findings indicating an infection in a patient exposed to a medicinal product. The terms "suspected transmission" and "transmission" are considered synonymous.

Any abnormal laboratory's result resulting as a grade 4 in the CTCAE version 4 will be considered as serious adverse event even if this event is not clinically relevant.

Whether or not corresponding to the above-mentioned criteria, any other adverse event considered as serious by any IMP, any healthcare professional or any investigator should be handled as a serious adverse event.

NB. Cases where a subject shows an AST or ALT $\geq 3 \times \text{ULN}$ or total bilirubin $\geq 2 \times \text{ULN}$ may need to be reported as SAEs.

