11.8.2. Adverse Events based on examinations and tests

Deterioration as compared to baseline in protocol-mandated (laboratory values, vital signs, etc...) should therefore only be reported as AEs if they fulfill any of the SAE criteria or are the reason for discontinuation of treatment with the investigational product.

If deterioration in a laboratory value/vital sign is associated with clinical signs and symptoms, the sign or symptom will be reported as an AE and the associated laboratory result/vital sign will be considered as additional information. Wherever possible the reporting investigator uses the clinical, rather than the laboratory term (eg, anemia versus low hemoglobin value). In the absence of clinical signs or symptoms, clinically relevant deteriorations in non-mandated parameters should be reported as AE(s). Any new or aggravated clinically relevant abnormal medical finding at a physical examination as compared with the baseline assessment will be reported as an AE.

NB. Cases where a subject shows an AST or ALT $\geq 3 \times \text{ULN}$ or total bilirubin $\geq 2 \times \text{ULN}$ may need to be reported as SAEs.

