11.9. EXPECTED ADVERSE EFFECTS OF RADIOTHERAPY

The adverse effects of radiotherapy depend on the localization of the sarcoma and the irradiated area.

The expected acute adverse effects of radiotherapy are the following:

- Fatigue;
- Subcutaneous, musculoskeletal and skin toxicities including dermatitis, enanthema, redness, ulceration, bleedings, desquamation, necrosis, osteonecrosis, myositis, pain and infection ;
- Edema.

According to the irradiated area, blood toxicity (such as decrease in red blood cells, anemia, decrease in platelets and white blood cells) and digestive toxicity (such as enteritis, diarrhea, nausea, vomitis and stenosis) may occur.

The adverse effects may occur several months after the end of treatment, including:

- Loss of skin suppleness, skin atrophy;
- Pain or modification of sensibility;
- Fibrosis;
- Necrosis;
- Induration of tissue;
- Wound complication after a surgery
- Joint stiffness
- Secondary cancer.

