#### **4.2.2 PATIENT CHARACTERISTICS AT BASELINE**

- Table 2.1. Demographic characteristics at baseline
- Table 2.2. Pregnancy and female reproductive status
- Table 2.3. General medical/clinical conditions at baseline
- Table 2.4 Description of medical and surgical history
  - Table 2.4.1 Medical and surgical history (Y/N) at baseline
  - Table 2.4.2 Medical and surgical history (pathology) at baseline
  - Table 2.4.3. Ongoing concomitant treatments at baseline
- Table 2.5. Descriptive statistics for hematological parameters at baseline
- Table 2.6. Descriptive statistics for biochemical parameters at baseline
- Table 2.7. Descriptive statistics for coagulation parameters at baseline
- Table 2.6. Descriptive statistics for serological parameters at baseline
- Table 2.6. Descriptive statistics for urinalysis parameters at baseline

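### Asymptomatic grade 1–3 laboratory changes are largely left out of the graded toxicity report, and the protocol contradicts itself on recording non-serious late radiotherapy toxicity

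*Protocol*

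**What the plan says.** **Laboratory changes.** Protocol 11.8.2 states that deteriorations from baseline in protocol-mandated tests "should therefore only be reported as AEs if they fulfill any of the SAE criteria or are the reason for discontinuation of treatment". If there are symptoms, the symptom is the adverse event and the laboratory value is supporting information. Section 11.2.2 supplies the automatic SAE route: any abnormal laboratory "result resulting as a grade 4 in the CTCAE version 4 will be considered as serious adverse event". For AST, ALT and bilirubin above set multiples of normal, both sections say only that SAE reporting may be needed.

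SAP 3.2.1.1 takes toxicity from the examination and adverse-event forms. SAP 4.2.2 plans laboratory tables at baseline only, for example "Table 2.5. Descriptive statistics for hematological parameters at baseline", and SAP 4.2.10 counts adverse events by term and by grade.

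**DLTs.** Protocol 3.3 has its own wording: "A DLT is defined as an adverse event (AE) or laboratory abnormality that fulfills all the criteria below". The general laboratory criterion is an abnormality of at least "grade 3 lasting > 5 days (except for lymphopenia, hyperglycaemia and changes in serum electrolytes/enzymes without clinical impact").

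**Late toxicity.** Protocol 5.6 ends adverse-event reporting 30 days after olaparib *and/or* 6 weeks after radiotherapy, or at a new antitumour therapy if earlier. It continues: "Beyond this period of time, only those SAEs suspected to be treatment-related (Olaparib/radiotherapy) or research-related" are to be reported. Section 3.3 bases the RP2D on the MTD and on "additional safety data, including acute and late toxicities, PK and PD data". Section 11.9 warns: "The adverse effects may occur several months after the end of treatment", and lists fibrosis, skin atrophy and joint stiffness among them.

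**The concern.** The safety profile and the RP2D are primary objectives of the escalation part, and CTCAE-graded toxicity is a primary endpoint beside DLT incidence. Section 1.2 names bone marrow as the target organ of toxicity, so most of the drug's expected signal is in blood counts, which are often abnormal without symptoms. A rule that keeps such values out of the adverse-event record, with an SAP that does not go back to the laboratory data, gives a graded profile thinner than the data collected.

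For a radiosensitiser, late in-field tissue damage is the other main risk. The RP2D rule calls for late toxicities, but one part of the protocol stops collecting them unless they are serious and related. Sites that read different sections would collect different data, and late event counts could not then be compared across sites or dose levels.

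**Working it through.** **1. Laboratory changes: the texts side by side**

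| Place | What it implies for an asymptomatic grade 1–3 value |
|---|---|
| Protocol 11.8.2 with 11.2.2 | Not an adverse event unless an SAE criterion is met or treatment is discontinued |
| Protocol 11.2.1 | Abnormal laboratory findings can be adverse events |
| Protocol 7.1.6.3 | Grade 1–2 anaemia is called an adverse event |
| Protocol 8.3 | Changes in laboratory parameters are part of the safety evaluation |
| SAP 4.2.2 and 4.2.10 | Laboratory tables at baseline only; safety tables count adverse events |

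Now follow an asymptomatic grade 3 neutrophil count that interrupts olaparib through the plan.

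- *Adverse event?* It is not grade 4, and an interruption is not a discontinuation, which 5.2 describes as ceasing to receive study medication. Under 11.8.2 the answer is no, so it is absent from SAP Tables 10.1 and 10.2.
- *DLT?* Yes if it lasts more than 5 days and meets the attribution criteria; it then goes to SAP Table 9.4. A toxicity-related olaparib interruption of 14 days or more is a DLT in its own right.
- *Treatment modification?* Protocol 7.1.6.7 requires interruptions and their reasons in the eCRF, and SAP Tables 7.1.1 and 7.4 report them by dose level.
- *What is lost?* For an event below the DLT threshold, the CTCAE grade. A grade 1–2 value with no change of treatment has no planned table at all if 11.8.2 is followed.

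The DLT flags (DLT_RA, DLT_ON) are entered on examination forms. SAP 3.2.1.1 checks only that they are completed, not that they agree with laboratory values. Scheduled counts on D15, D29 and D43 are 14 days apart (29 − 15 = 43 − 29 = 14). A single scheduled value therefore cannot show whether an abnormality lasted more than 5 days. Start and stop dates are collected with each adverse event (11.7), and that is the record 11.8.2 removes.

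**2. Late toxicity: the length of the gap if 5.6 is followed**

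Inputs: radiotherapy starts at D8 (taken as a Monday), 33 fractions at 5 per week, olaparib stopped with radiotherapy, 12 months of follow-up taken as 365 days from D1.

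- Plan's own figure: 1 + 6.5 + 6 = 13.5 weeks for the DLT window (3.4.1). Reproduced.
- Last fraction: six full weeks give 30 fractions; fractions 31 to 33 fall on D50, D51 and D52. This matches the protocol's D52.
- Six-week window closes: 52 + 42 = D94.
- Days left: 365 − 94 = 271 (271/365 = 74%).
- Counting the toxicity check four weeks after treatment discontinuation (5.2): 94 + 28 = D122; 365 − 122 = 243 days (67%).
- If *and/or* is read as 30 days after olaparib: 52 + 30 = D82, which is 94 − 82 = 12 days before the DLT window closes.

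Against 5.6 stand section 11.1 and the schedule of assessments, both of which have adverse events recorded throughout the study.

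**The case against.** The strongest reply is that the protocol covers more than 11.8.2 and 5.6 suggest, and much of it stands.

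- **DLTs.** A reader might infer that DLT counts, and so dose allocation, depend on adverse-event recording. The documents do not support that. A laboratory abnormality can be a DLT without being an adverse event, and laboratory DLTs have their own variables, a listing (SAP 4.1.3) and Table 9.4. Grade 1–2 values do not enter the laboratory criterion, and toxicity arising after the DLT window cannot be a DLT. Only an indirect risk remains, because the flags are not checked against the data.
- **Visibility.** A reader might also infer that an asymptomatic grade 3 cytopenia that interrupts olaparib appears in no table. It does appear, as an interruption with a reason, and as a DLT if it qualifies. Its grade does not appear otherwise.
- **Late toxicity.** It would be too strong to say that late toxicity is not captured. Section 11.1 and the schedule say otherwise, and 11.8.2 itself makes new clinically relevant examination findings adverse events. Related SAEs have no time limit, events of special interest are collected whether serious or not, and surgical complications are reported for 12 months. Section 5.2 follows grade 3–4 toxicity to resolution. This makes the problem a contradiction rather than a plain omission. It does not settle which text sites will follow, and none of the special routes covers new non-serious fibrosis or stiffness in a patient without surgery.
- **The 74%.** This is not a trial-wide figure. It does not apply to patients who continue olaparib or to the 25-fraction schedule.

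**Conclusion.** The point holds in two limited parts.

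1. Following 11.8.2 and the SAP as written under-reports the graded haematological profile, because asymptomatic grade 1–3 changes mostly do not become adverse events and no post-baseline laboratory grade table is planned. The extent cannot be estimated, since the documents give no expected rates. The effect on DLT ascertainment is indirect only.
2. The protocol gives two incompatible rules for non-serious toxicity after the reporting window. If 5.6 prevails, new non-serious late in-field effects go uncollected for about 271 of 365 days, or about 243 with the 5.2 check. That holds for a patient given 33 fractions who stops olaparib at D52, on the six-week reading of *and/or*. The gap is shorter if olaparib continues. It is also up to 7 days shorter if the 12 months run from registration, since treatment starts within a week of it.

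The first part bears on the safety profile, the second on the RP2D. No sample size or decision threshold is affected. The changes should be made, but the design does not fail without them.

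**What to change.** **(a) Laboratory data.** In the SAP, derive the CTCAE grade from the scheduled post-baseline values and tabulate worst on-treatment grade and shift from baseline by dose level. This assumes those values are in the CRF; the SAP names haematology variables only on the pre-treatment form, so confirm it first. List grade 3 or higher values against the existing laboratory DLT criterion, with its exemptions and its more-than-5-days rule, as a check on the DLT flags. Sending every such value to DLT adjudication would ignore those limits. The exemption list must first be reconciled, because protocol 3.3 includes lymphopenia and SAP Table 9.4 does not. Reconcile 11.8.2 with 11.2.1, 7.1.6.3 and 8.3.

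**(b) Late toxicity.** Reconcile protocol 5.2, 5.6, 11.1 and the schedule, and state what *and/or* means. Record treatment-related late toxicity with its CTCAE grade at the existing three-monthly visits to month 12; these already include physical examination and assessment of symptoms. Report it descriptively as counts by dose level. With 24 assessable escalation patients over four levels and 14 in expansion, finer analysis would be too sparse to read.

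**Cost.** Some programming for (a), a small amount of extra data entry for (b), and a protocol amendment to align the sections. No added visits or tests.

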11.8.3. New cancers

The development of a new primary cancer should be regarded as an AE and will generally meet at least one of the serious criteria (see Section 11.2.2). New primary cancers are those that are not the primary reason for the administration of the study treatment and have developed after the inclusion of the patient into the study. They do not include metastases of the original cancer.

11.9. EXPECTED ADVERSE EFFECTS OF RADIOTHERAPY

The adverse effects of radiotherapy depend on the localization of the sarcoma and the irradiated area.

The expected acute adverse effects of radiotherapy are the following:

- Fatigue;
- Subcutaneous, musculoskeletal and skin toxicities including dermatitis, enanthema, redness, ulceration, bleedings, desquamation, necrosis, osteonecrosis, myositis, pain and infection ;
- Edema.

According to the irradiated area, blood toxicity (such as decrease in red blood cells, anemia, decrease in platelets and white blood cells) and digestive toxicity (such as enteritis, diarrhea, nausea, vomitis and stenosis) may occur.

The adverse effects may occur several months after the end of treatment, including:

- Loss of skin suppleness, skin atrophy;
- Pain or modification of sensibility;
- Fibrosis;
- Necrosis;
- Induration of tissue;
- Wound complication after a surgery
- Joint stiffness
- Secondary cancer.

11.10. RESPONSIBILITY OF VIGILANCE UNIT

The Vigilance Unit will analyze each SAE to define:

- The relationship with the study treatment,
- The listedness/expectedness according to the most updated reference safety information of the studied treatment Investigator's Brochure (IB) for Olaparib, protocol for radiotherapy (see section 11.8).

11.11. NOTIFICATION AND REGISTRATION OF UNEXPECTED SERIOUS ADVERSE EVENTS AND NEW INFORMATION (RESPONSIBILITY OF THE SPONSOR)

The sponsor notifies unexpected serious adverse events and new information to the Regulatory Authorities (in person, or through an organization which has received allowances for this task) according to the usual notification procedures.

12. QUALITY ASSURANCE AND TRIAL MONITORING

12.1. MONITORING OF THE TRIAL

12.1.1. Steering Committee

The study will be supervised and monitored by a Steering Committee comprising members participating in the study:

- Dr [name], Co-ordinating Investigator and Chairman of the Committee,
- Pr [name], Investigator and medical oncologist, (or a substitute)
- A representative of the sponsor (Pr [name] or a substitute).
- The biostatistician of the trial (Ms. [name], or a substitute).
- The pharmacist of the trial ([name], or a substitute).
- Co-ordinating Clinical research assistant ([name] or a substitute)

This committee must ensure the following:

- Implementation and regular follow-up of the study
- Patient protection,
- That the trial is conducted ethically, in accordance with the protocol,
- That the trial benefit/risk ratio is evaluated and the scientific results are checked during or at the end of the trial.

It decides on any relevant amendment to the protocol that is required in order to continue the trial (protocol amendments prior to submission to the EC and the relevant Health Authorities, decisions on whether to open or close research sites, discussion of results and the strategy for the publication of these results). It must inform the sponsor of any decisions taken. Decisions concerning a major amendment or a change to the budget must be approved by the sponsor.

